13.5 Analysis Populations

13.5.1 Intention-to- treat and per protocol population

ITT population: The intention-to-treat (ITT) population includes all randomized patients who received at least one dose of the study drug. Analysis of the ITT population will be done according to the initial treatment assigned to the patient (as randomized). ITT population may be used for sensitivity analysis of the efficacy endpoints, as well as for analysis of data including (but not limited to) demographics and baseline characteristics.

PP population: The per protocol population set (PPS) includes all ITT patients who did not have any relevant major protocol deviations, e.g., patients who are randomized and treated, but do not have laboratory-confirmed SARS-CoV-2 infection will be excluded from PPS. Analysis of the PPS will be done according to the treatment the patient

actually received (as treated). The PPS will be used for sensitivity analysis of the primary efficacy endpoint.

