Duration of Treatment: Subjects randomized to receive BMS-986253 will receive treatment for up to 4 weeks while hospitalized or intolerable toxicity or side effects. Patients who are discharged prior to 2 weeks after the first treatment, will not receive additional doses of therapy. Patients still with severe respiratory symptoms and hospitalized at 4 weeks may receive an additional treatment dose. Subjects randomized to the control arm will receive standard of care therapy as determined by their treating physician.

PK assessments and Correlative Studies: Serum will be collected at baseline and then weekly during hospitalization if feasible. For patients ready for discharge prior to day 8, a serum sample should be collected, when feasible, prior to discharge.

Duration of Follow up: Toxicity and laboratory tests will be graded using the NCI CTCAE v5.0 scoring system. Adverse events will be assessed continuously from the inpatient medical record during the study and for **100 days** after the last dose of treatment. Laboratories as outlined in **Section 11** will be collected daily during hospitalization. Post-discharge medical history and survival will be assessed monthly until 100 days following the last dose of therapy and then every 3 months for up to 1 year.

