13.2 Study Endpoints and Analysis Plan

All subjects who receive at least one dose of study drug will be considered evaluable and included in the efficacy and safety analysis.

Analytic plan for primary objective:

The primary efficacy null hypothesis of the equality of time to improvement (2 points) in clinical status curves will be tested with the log-rank test. The overall type I error for the primary analysis will be considered one-sided alpha of 0.025. Kaplan-Meier estimates will be reported for each of the two arms with median time to improvement and 95% confidence intervals (CI). Cox regression will be employed to estimate the treatment effect (HR) and 95% CI.

Analytic plan for secondary and exploratory objective:

We will estimate the distributions of all time-to-event endpoints using the Kaplan-Meier method and if possible, provide medians (95% CI). Comparisons between survival curves will be assessed using log-rank tests and Cox regression models.

For each arm, we will estimate the 1-month mortality rate and incidence of adverse events graded by CTCAE v5.0 using the exact 95% confidence intervals. Comparisons between the two arms will be assessed using chi-squared or Fisher's exact tests. The mean/medians of the 7-point ordinal scores at day 14 after the start of treatment will be computed and compared between the two groups using two-sample t-test or the equivalent non-parametric Wilcoxon Rank-Sum test if normality is not satisfied.

Changes in exploratory endpoints (before and after treatment) will be quantified using means (95% CI) and/or medians (inter-quartile ranges) for non-normal data. Comparisons between the two arms will be made using two-sample independent t-tests or the non-parametric equivalent, Wilcoxon Rank-Sum test. The associations between baseline levels and/or changes over time of IL-8 and other key cytokines (TNF, IL-1b, IL-6) with outcomes will be assessed using regression models.

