13.4 Interim analyses

One interim analysis is planned after approximately 17 (40% of the total 41 events) have been observed using O'Brien and Fleming stopping boundary using the Lan-DeMets spending function at a nominal type I error of 0.025. The intent-to-treat (ITT) principle is applied to the analysis, and therefore, we inflated the sample size by 5% to safeguard against drop-outs.

An independent Data Safety Monitoring Committee (DSMC) will serve as the primary reviewer of the results of the interim analyses of the study and will make recommendations for discontinuation of the study or protocol modifications. Stopping rules for overwhelming efficacy and/or futility are provided in Table 4 below.

Table 4. Efficacy and Boundaries and Properties for the Time to Improvement Analysis

Analysis*	Value	Efficacy	Futility
IA1: 40%	Nominal critical point Z-value	3.3569	0.0811
N: 138	p (1-sided)	0.0004	0.4677
Events: 17	~HR at bound	0.1720	0.9584
Month: 2.6	P(Cross) if HR=1	0.0004	0.5323
	P(Cross) if HR=0.4	0.0599	0.0427
IA2: 100%	Nominal critical point Z-value	1.9622	1.9622
N: 138	p (1-sided)	0.0249	0.0249
Events: 41	~HR at bound	0.5217	0.5217
Month: 7	P(Cross) if HR=1	0.0240	0.9760
	P(Cross) if HR=0.4	0.8000	0.2000

*This column displays the number of events and percentage (%) of needed time to improvement events, the expected sample size (N), and the estimated months (Month) after first participant is randomized for each analysis.

p (1-sided): the nominal α for testing.

~HR at bound: the approximate hazard ratio required to reach the bound for overwhelming efficacy or futility stop.

P (Cross if HR=1): the probability of crossing a bound at or before each analysis under the null hypothesis.

P (Cross if HR=0.40): the probability of crossing a bound at or before each analysis under the alternative hypothesis.

Abbreviations: HR = hazard ratio; IA = interim analysis.

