13.5.2 Safety population

The safety population includes all randomized patients who received at least one dose of the study drug. Analysis of the Safety population will be done according to the treatment received (as treated).

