13.6 Safety Analysis

All subjects receiving at least one dose of the study drug will be evaluated for safety by monitoring symptoms, physical examinations, and laboratory tests. Adverse events will be classified and graded according to the NCI Common Toxicity Criteria version 5.0 (see Appendix B). The absolute number and frequency of each adverse event will be reported, and subdivided according to toxicity grade. A description of adverse events by treatment arm will also be reported. A particular adverse event occurring more than once in the same subject will be counted only once and at its worse grade. At the end of study, the cumulative incidences of these events will be compared between the two treatment groups using Fisher's exact test.

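### Every analysis set requires a dose of study drug that controls never receive, and the primary clock has no defined start for controls

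*Combined protocol and SAP*

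**What the plan says.** Membership of the analysis sets is stated in these places:

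- Section 13.2, for efficacy and safety: "All subjects who receive at least one dose of study drug will be considered evaluable and included in the efficacy and safety analysis".
- Section 13.5.1, ITT: "The intention-to-treat (ITT) population includes all randomized patients who received at least one dose of the study drug". These patients are analysed as randomised, but the set has only an optional role: "ITT population may be used for sensitivity analysis of the efficacy endpoints".
- Section 13.5.1, per protocol: "The per protocol population set (PPS) includes all ITT patients who did not have any relevant major protocol deviations".
- Section 13.5.2: "The safety population includes all randomized patients who received at least one dose of the study drug".
- Section 13.6, and in the same terms 11.2.5: "All subjects receiving at least one dose of the study drug will be evaluated for safety".

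On the comparator, Section 4.1 says: "Subjects randomized to the control arm will receive standard of care therapy as determined by their treating physician". Section 9 lists BMS-986253 as the only study drug, and no crossover is described.

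The synopsis and Section 13.4 nevertheless state: "The intent-to-treat (ITT) principle is applied to the analysis". Section 13.2 plans a two-arm log-rank test, Kaplan-Meier estimates by arm and a Cox model. Section 13.6 plans Fisher's exact test between arms.

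On timing, Sections 4.1, 11.1.1 and 13.1 run the primary endpoint from start of treatment, while the objectives (synopsis and Section 2) run it from baseline. Neither is given a date for a control. The screening window in the study calendar (note a) is itself tied to the BMS-986253 dose. Section 11.2 also runs 1-month mortality, improvement in oxygenation and the day-14 score from start of treatment. In Section 8.2, adverse-event collection opens when study drug is started and closes 100 days after the last dose.

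**The concern.** Taken as written, no set contains a control patient, so the planned comparisons have no comparator. The plan also contradicts itself: it invokes the ITT principle, defines ITT by dosing, and then reserves that set for possible sensitivity use. The only set named for the main efficacy analysis is the dose-based one in 13.2.

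Adding controls back does not cure this. The dose condition would then act on the anti-IL-8 arm alone, removing patients who improve, deteriorate or withdraw between randomisation and first dose, while their counterparts in the control arm stay in. Section 6.1 itself foresees patients who withdraw before protocol therapy begins. Because the trial is open-label, the choice of repair and of the control start date would be made after data exist and with assignments known.

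The clock is a separate gap. If treated patients are timed from first dose and controls from randomisation, the arms start at different points in the illness. Post-discharge adverse events could also be counted over different periods in the two arms.

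**Working it through.** **1. The plan's own figure.** Inputs: HR 0.40, one-sided alpha 0.025, power 80%, 2:1 allocation (Section 13.1), 41 events (Section 13.4).

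- Schoenfeld events = (1.960 + 0.842)² / [(2/3)(1/3)(ln 0.40)²] = 7.849 / 0.1866 = 42.07, rounded up to 43, against 41 stated.
- Power at 41 events = Φ(√(41 × 2/9) × 0.916 − 1.960) = Φ(0.806) = 79%, against 80% stated.

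The design therefore assumes that both arms are analysed at 92 and 46.

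**2. Literal reading.** The sets hold at most 92 anti-IL-8 patients and 0 of 46 controls. The treated share is a = 1, so information per event is a(1 − a) = 0, against 2/9 as planned. The log-rank, Cox and Fisher comparisons cannot be computed.

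**3. Repaired readings, no true effect.** The documents give neither a randomisation-to-dose delay nor an observed hazard shape, so both are varied as assumptions. Set-up: 92 against 46, control median 5 days (synopsis), accrual uniform over 210 days (Table 4 puts the final analysis at month 7), follow-up to day 28, rejection at Z > 1.96, 10,000 runs. Simulation standard error near 2.5% is √(0.025 × 0.975 / 10,000) = 0.16 points. Rejection rates at 41 events, in %, by Weibull shape (1 = constant hazard):

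| Analysis | 0.7 | 1 | 1.5 | 2 |
|---|---|---|---|---|
| All randomised, both clocks at randomisation | 2.0 | 2.4 | 2.3 | 2.3 |
| Dosed only, both clocks at randomisation, delay uniform 0–1 day | 0.8 | 1.3 | 1.8 | 2.1 |
| Same, delay fixed at 1 day | 0.3 | 0.7 | 1.5 | 1.9 |
| Dosed only, drug clock at dose, control clock at randomisation, delay uniform 0–1 day | 1.2 | 2.5 | 4.4 | 6.1 |
| Same, delay fixed at 1 day | 0.9 | 2.4 | 6.2 | 12.9 |

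Rows 2 and 3 drop active patients who improve before dosing, which works against the drug.

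A further case uses constant hazard with both clocks at randomisation. Here 2%, 5% or 10% of patients deteriorate early; they are dropped from the active arm but kept as non-improvers to day 28 in control. Rejection is 3.2%, 6.1% and 12.3%. If such controls are instead censored at death, it is 2.1% to 2.4%.

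**4. Sensitivity of these figures.** With all 138 patients analysed, a split clock and a fixed 1-day delay, rejection is 0.4%, 2.5%, 12.7% and 29.9% across the four shapes. The early-deteriorator case becomes 5.7%, 14.6% and 36.4%, with the all-randomised set at 2.1% to 2.4%. Section 13.1 gives the control median as 2 days, the reverse of the synopsis. At 2 days with full follow-up, the split clock gives 2.7% to 2.8% under constant hazard. For shapes 1.5 and 2 it gives 16.3% and 42.6% at a half-day delay, and 38.2% and 89.9% at one day.

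**5. Power.** Constant hazard, improvement hazard multiplied by 1/0.40 = 2.5 from dosing onward:

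| Analysis | No delay | Uniform 0–1 day | Fixed 1 day |
|---|---|---|---|
| All randomised, 41 events | 71.6% | 65.1% | 57.2% |
| Dosed only, randomisation clock, 41 events | 71.8% | 61.4% | 50.1% |
| All randomised, all 138 followed to day 28 (4,000 runs) | 99.8% | 99.2% | 98.3% |

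The no-delay power at 41 events is below the plan's 80%, so the differences between columns are the useful part.

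**The case against.** The strongest reply is that the intent is not in doubt. Section 13.5.1 says as randomised, 13.2 and 13.6 plan two-arm comparisons, and no analyst would leave the controls out. That stands: the count of 0 of 46 describes the wording and is not a realistic outcome.

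The error rates can also be challenged:

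- Exponential times are the plan's own assumption (13.1), and under them a split clock gives no inflation.
- Screening within 1 day of dosing and real-time randomisation (7.5) make a delay beyond about a day unlikely, so the fixed 1-day rows are a worst case. With a 0.25-day or uniform 0–0.5 day delay and a 5-day median, shapes 1.5 to 2 give only 3.1% to 3.7%.
- The early-deteriorator case depends on how those controls are censored, and its 10% level is twice the plan's 5% drop-out allowance.
- Under the simulation's inputs, 41 events arrive with only about 44 to 51 patients enrolled, whereas Table 4 shows 138.

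These points properly limit the figures to illustration.

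Finally, 8.2 also speaks of a reporting period opening with any study procedure, 10.1 ties baseline to starting the protocol, and 10.2 reviews toxicity daily in hospital in both arms. This narrows the adverse-event gap without closing it: the example given in 8.2 is still the first dose, and the 100-day tail has no control equivalent. Nothing in the documents supplies a set that contains controls or a start date for them.

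**Conclusion.** The concern holds and must be fixed. The plan names no primary efficacy set containing both arms, contradicts its own ITT statement, and gives no common start for the primary clock or for the other endpoints timed from start of treatment. Time to death and time to intubation (from symptom onset) and duration of hospitalisation (from admission) do not share the clock problem.

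This conclusion rests on the text alone. The direction and size of any bias are not fixed by the documents. Depending on the repair, the dosing delay, the hazard shape and the handling of early deterioration, the error can fall below 2.5%, stay near it or exceed it several-fold. Of the analyses simulated, only the all-randomised set timed from randomisation stayed near nominal throughout.

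**What to change.** - Define ITT as all randomised patients, analysed as randomised, and name it in 13.2 as the primary efficacy set.
- Use randomisation as day 0 in both arms for the primary endpoint, 1-month mortality, oxygenation and the day-14 score.
- Define the safety set as dosed anti-IL-8 patients plus controls not given study drug, with adverse events counted from randomisation over one fixed window in both arms. Events before first dose would then count in the drug arm and should be flagged.
- Keep the dosed-only comparison as a sensitivity analysis.

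The cost is mainly wording: synopsis, 2, 4.1, 7.7, 8.2, 8.4.4, the calendar notes and 10.3, 11.1, 11.2, 13.1, 13.2, 13.5 and 13.6, plus a stated adverse-event window for controls. N = 138 and 41 events do not change.

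Starting the clock at randomisation dilutes the effect by any dosing delay. At 41 events the simulated loss is 71.6 − 65.1 = 6.5 points for a uniform 0–1 day delay and 71.6 − 57.2 = 14.4 points for a fixed 1-day delay. The dosed-only set on the same clock loses more: 71.8 − 61.4 = 10.4 and 71.8 − 50.1 = 21.7 points. If all 138 patients are followed to day 28, all-randomised power stays at 98% or above.

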13.5.2 Safety population

The safety population includes all randomized patients who received at least one dose of the study drug. Analysis of the Safety population will be done according to the treatment received (as treated).

13.6 Safety Analysis

All subjects receiving at least one dose of the study drug will be evaluated for safety by monitoring symptoms, physical examinations, and laboratory tests. Adverse events will be classified and graded according to the NCI Common Toxicity Criteria version 5.0 (see Appendix B). The absolute number and frequency of each adverse event will be reported, and subdivided according to toxicity grade. A description of adverse events by treatment arm will also be reported. A particular adverse event occurring more than once in the same subject will be counted only once and at its worse grade. At the end of study, the cumulative incidences of these events will be compared between the two treatment groups using Fisher's exact test.

13.4.1 Evaluation of adverse events

Treatment-emergent adverse events will be translated from investigator terms to MedDRA version 22.1 terminology and summarized (number and percentage of patients) for all patients who receive at least one dose of the study drug(s). Adverse event summaries will be organized by body system, frequency of occurrence, intensity (*i.e.*, severity grade), and causality or attribution. Patients who experience an adverse event more than once will be counted only once. The occurrence with the maximum severity will be used to calculate intensity.

13.4.2 Evaluation of serious adverse events and premature withdrawals

Adverse events deemed serious and those resulting in early treatment withdrawal or death will be summarized separately. Narrative paragraphs will be generated to describe the circumstances surrounding each SAE and each death.

13.4.3 Evaluation of laboratory parameters and assays

Abnormal laboratory parameters (*e.g.* electrolyte levels, liver function tests, renal function tests, complete blood counts) will be summarized, and clinically significant changes from baseline will be discussed.

14 PROTECTION OF HUMAN SUBJECTS

This study is to be conducted in accordance with applicable government regulations and Institutional research policies and procedures.

This protocol and any amendments will be submitted to a properly constituted Institutional Review Board (IRB), in agreement with local legal prescriptions, for formal approval of the study conduct. The decision of the IRB concerning the conduct of the study will be made in writing to the investigator and a copy of this decision will be obtained before commencement of this study.

All subjects for this study will be provided a consent form describing this study and providing sufficient information for subjects to make an informed decision about their participation in this study. This consent form will be submitted with the protocol for review and approval by the IRB for the study. The formal consent of a subject, using the IRB-approved consent form, must be obtained before that subject is submitted to any study procedure. This consent form must be signed by the subject or legally acceptable surrogate, as outlined in the IRB approved protocol, and the investigator-designated research professional obtaining the consent.

The PI, co-investigators and research nurses will conduct a remote consent discussion with the subject. Eligible study participants will be given detailed information about the study purpose, procedures, and requirements. The research team will be available to answer all the patients' questions adequately before he/she decides to enroll in the study. It will be emphasized to patients that enrolling in the study may or may not directly benefit them, nor will choosing not to participate affect their treatment or care in any way. Patients will be informed that the information collected from their medical records, specimens, and blood samples will be kept confidential. Each patient will be assigned a study ID number to which all study information will be linked. Patients will be assured that the only document linking their personal identification information to this number will be kept in a locked secure location. We will enroll non-English speaking participants. Non-English speaking participants will be enrolled in accordance with the CUMC IRB enrollment of non-English speaking subjects' policy.

15. STUDY FINANCES

15.1 Conflict of Interest

Any investigator who has a conflict of interest with this study (patent ownership, royalties, or financial gain greater than the minimum allowable by their institution, etc.) must have the conflict reviewed by the Columbia University Conflict of Interest Committee with a Committee-sanctioned conflict management plan that has been reviewed and approved prior to participation in this study. All CUMC investigators will follow the University conflict of interest policy.

16 PUBLICATION PLAN

Neither the complete nor any part of the results of the study carried out under this protocol, nor any of the information provided by the sponsor for the purposes of performing the study, will be published or passed on to any third party without the consent of the study sponsor. Any investigator involved with this study is obligated to provide the sponsor with complete test results and all data derived from the study.

18 ATTACHMENTS

APPENDIX A: COMMON TOXICITY CRITERIA, VERSION 5.0

Adverse events will be described and graded using the NCI Common Toxicity Criteria (Version 5.0). A copy of this document can be downloaded from the CTEP website (https://ctep.cancer.gov/protocolDevelopment/electronic_applications/ctc.htm). All treatment areas must have a copy of this document, or must be able to access a copy.

In general, the grading system can be summarized as follows:

Grade:	Severity:	Description:
Grade 1	Mild	Mild; asymptomatic or mild symptom; clinical or diagnostic observation only; intervention not indicated.
Grade 2	Moderate	Moderate; minimal, local or noninvasive intervention indicated; limiting age-appropriate instrumental ADL.
Grade 3	Severe	Severe or medically significant but not immediately life-threatening; hospitalization or prolongation of hospitalization indicated; disabling; limiting self-care ADL.
Grade 4	Life-threatening	Life-threatening consequences; urgent intervention indicated.
Grade 5	Death	Death related to an adverse event.

APPENDIX B: NATIONAL EARLY WARNING SCORE 2 (NEWS2)

Chart 1: The NEWS scoring system

Physiological parameter	Score						
	3	2	1	0	1	2	3
Respiration rate (per minute)	≤8		9–11	12–20		21–24	≥25
SpO ₂ Scale 1 (%)	≤91	92–93	94–95	≥96			
SpO ₂ Scale 2 (%)	≤83	84–85	86–87	88–92 ≥93 on air	93–94 on oxygen	95–96 on oxygen	≥97 on oxygen
Air or oxygen?		Oxygen		Air			
Systolic blood pressure (mmHg)	≤90	91–100	101–110	111–219			≥220
Pulse (per minute)	≤40		41–50	51–90	91–110	111–130	≥131
Consciousness				Alert			CVPU
Temperature (°C)	≤35.0		35.1–36.0	36.1–38.0	38.1–39.0	≥39.1	

